[figure not shown]

## NON-INTERVENTIONAL (NI) STUDY PROTOCOL

### Study Information

Title	Clinical Outcomes of Early Versus Delayed Management of Iraqi Patients With ankylosing spondylitis (AS) With Etanercept
Protocol number	B1801415
Protocol version identifier	3.0
Date	29 July 2021
Active substance	Etanercept
Medicinal product	Etanercept
Research question and objectives	Many publications found that the early initiation of biological treatment had positive impact on patients' response to the treatment regimen, and with this Real World Data (RWD), our objective is to evaluate the impact of early initiation of etanercept on patient-response compared to delayed introduction of biological treatment.
Author	PPD – MD, M.Sc. PPD Pfizer Inc. – Iraq
This document contains confidential information belonging to Pfizer. Except as otherwise agreed to in writing, by accepting or reviewing this document, you agree to hold this information in confidence and not copy or disclose it to others (except where required by applicable law) or use it for unauthorized purposes. In the event of any actual or suspected breach of this obligation, Pfizer must be promptly notified.	

PFIZER CONFIDENTIAL

A thick black horizontal bar redacting sensitive information.

**PFIZER CONFIDENTIAL**

## 2. LIST OF ABBREVIATIONS

Abbreviation	Definition
ACR	American College of Rheumatology
AE	Adverse Event
Anti-CCP	Anti-Cyclic Citrullinated Peptide
AS	Ankylosing Spondylitis
BASDAI	Bath Ankylosing Spondylitis Disease Activity Index
BASFI	Bath Ankylosing Spondylitis Functional Index
DMARDs	Disease-Modifying Antirheumatic Drugs
EULAR	European League Against Rheumatism
GEP	Good Epidemiological Practice
GPP	Guidelines for Good Pharmacoepidemiology Practices
HLA-B27	Human Leukocyte Antigen B27
IEA	International Epidemiological Association
IEC	Independent Ethics Committee
IRB	Institutional Review Board
ISPE	International Society for Pharmacoepidemiology
ISPOR	International Society for Pharmacoeconomics and Outcomes Research
N/A	Not Applicable
NI	Non-Interventional
NSAIDs	Nonsteroidal Anti-Inflammatory Drugs
RA	Rheumatoid Arthritis

PFIZER CONFIDENTIAL

Abbreviation	Definition
RWD	Real World Data

PFIZER CONFIDENTIAL

#### **4. AMENDMENTS AND UPDATES**

Amendment number	Date	Protocol section(s) changed	Summary of amendment(s)	Reason
1	08 July 2021	Section 5. Milestones	Updated to align with Study Report	Administrative
2	29 July 2021	Throughout document	Spelling errors	Administrative
		Section 5 Milestones	Updated to align with Study Report	Administrative

**PFIZER CONFIDENTIAL**

## 5. MILESTONES

Milestone	Planned date
Start of data collection	01 August 2020
End of data collection	01 October 2020
Final study report	01 September 2021

## 6. RATIONALE AND BACKGROUND

In the past 1–2 decades, treatment paradigms in Ankylosing Spondylitis (AS) have shifted dramatically from initial treatment with nonsteroidal anti-inflammatory drugs (NSAIDs), followed by the cautiously progressive addition of disease-modifying antirheumatic drugs (DMARDs), to the current treatment approach of the aggressive initiation of DMARD therapy soon after the diagnosis of AS has been made. This change in AS management results from increasing data supporting improved prognosis and outcomes with the initiation of DMARD therapy early in the course of symptomatic disease. Since the goals in AS management include not only disease remission but also improved functional status, which is strongly associated with radiographic joint damage, an understanding of the impact that the initiation of appropriate treatment during early AS has on these outcomes is essential.

Accurate diagnosis of early AS begins with clear definitions of AS, as there is considerable variability in the literature regarding the time frame defining early AS. Previous intervention studies in early AS have included early AS as disease duration from 3 months to 3 years; however, with the knowledge of improved outcomes with earlier treatment in AS, it becomes clear that a shorter time interval for classification of early rheumatoid arthritis (RA) is clinically significant. Due to the wide range of definitions of early AS presented in the literature, it is difficult to characterize the specific time frame that defines early AS.

Multiple studies have evaluated the benefits of early treatment of AS, including several that have evaluated the impact of early DMARD treatment on successful response to therapy. In particular, a meta-analysis of ~1,400 AS patients from 14 randomized controlled trials identified that one of the strongest predictors of response to therapy was a shorter disease duration at the time of treatment initiation.

## 7. RESEARCH QUESTION AND OBJECTIVES

The objective of this study is to evaluate the impact of early initiation of etanercept on patient response compared to delayed introduction of biological treatment.

## 8. RESEARCH METHODS

### 8.1. Study Design

- **Retrospective analysis** of patients with AS that received etanercept from Baghdad teaching hospital (Rheumatology center) from August 2012 until March 2020 (inclusion and exclusion criteria will apply for selecting patients).
- **Primary objective:** determine the clinical impact of early referral for management in patients with AS compared to delayed management.
- **Secondary objective:** determine the influence of early referral on the response to biological treatment.

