### 8.2. Setting

#### Patients and Methods

Data will be collected from the Baghdad Teaching Hospital registry. The rheumatology patient registry is a prospective longitudinal multicenter cohort initiated in 2012. It captures all patients treated with biologic therapies managed in the rheumatology department. The decision to initiate and maintain the treatment is guided by the American College of Rheumatology (ACR) recommendations.

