### **8.3. Data Sources**

Patients will be identified from the rheumatology patient registry with rheumatoid arthritis and will obtain information on patient demographics (age, gender), education level (years), present smoking status, disease duration (years), current steroid therapy (yes/no), baseline bath ankylosing spondylitis disease activity index (BASDAI), Bath Ankylosing spondylitis functional index (BASFI), human leukocyte antigen B27 (HLA-B27), anticitrullinated protein antibody (anti-CCP) status.

Primary Outcomes: Disease activity Index BASFI and BASDAI from the last follow-up visit.

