### **8.6. Data Analysis**

All covariates will be summarized to get information about frequency distribution and mean, median or standard deviation. Numbers and percentages will be provided for categorical variables when performing descriptive analysis. Means, medians, standard deviations, or interquartile range as appropriate will be provided for continuous variables when performing descriptive analysis of continuous data.

Patients will be divided according to the mean of disease duration groups (below and above mean) and unadjusted comparisons between groups of the covariates and they will be evaluated using appropriate tests: chi-squared test will be used for categorical variables, t-test will be used for continuous variables, and the Kruskal-Wallis test for non-parametric variables; p-values will be generated.

We will determine the effect of early referral on the biologic treatment response patients with AS a multivariate analysis by using a stepwise linear regression model. The response variable is defined as BASFI and BASDAI at last visit. The baseline variables are considered demographic data, disease duration (years), methotrexate (yes/no), Current steroid therapy (yes/no), baseline BASFI, BASDAI, HLA-B27 positive (yes/no), anti-CCP (yes/no), present smoking (yes/no).

We will determine the effect of early response by using the difference in change between the baseline of BASDAI and BASFI and last follow-up. P-value <0.05 will be considered statistically significant.

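### The primary objective asks about early referral, but the planned data and analyses can only address how response to etanercept varies with disease duration

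*Combined protocol and SAP*

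**What the plan says.** **Question.** The primary objective in Section 8.1 is to "determine the clinical impact of early referral for management in patients with AS compared to delayed management". The Section 8.2 hypothesis is one of no difference in response between early and delayed referral. Section 7 is worded differently: it concerns early initiation of etanercept and patient response.

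**Population.** Section 8.1 takes "patients with AS that received etanercept from Baghdad teaching hospital (Rheumatology center) from August 2012 until March 2020". Section 8.2.2 excludes anyone with less than one year of use. The registry is one of treated patients: "It captures all patients treated with biologic therapies" (Section 8.2).

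**Groups.** Section 8.6: "Patients will be divided according to the mean of disease duration groups (below and above mean". No other definition of early or delayed is given. Section 8.3 lists disease duration in years but no referral date, and does not say at what moment duration is measured.

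**Outcome and analysis.** Section 8.3: "Primary Outcomes: Disease activity Index BASFI and BASDAI from the last follow-up visit". Section 8.6 repeats this for the regression: "The response variable is defined as BASFI and BASDAI at last visit". The effect of early referral is to come from "a multivariate analysis by using a stepwise linear regression model", whose candidate variables include "disease duration (years), methotrexate (yes/no), Current steroid therapy (yes/no), baseline BASFI, BASDAI". Section 8.6 also plans a comparison of change from baseline to last follow-up.

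**Limitations.** Section 8.8 names missing data and nothing else.

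**The concern.** The impact of early referral is a causal contrast: the same patient, referred early or late, judged at a comparable point in the disease. The plan has no such comparison. Patients with longer disease are scored at a later disease age, and everyone is already on etanercept. A worse last-visit score in the longer-duration group could come from later treatment, from the extra years of disease, or from both. Section 6 itself links functional status to radiographic joint damage, so accumulation over disease years is a plausible rival explanation, for BASFI above all. Entering disease duration as a covariate does not separate the two, because disease duration is the exposure.

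At stake is the headline conclusion. A difference in last-visit level could be reported as a clinical impact of early referral when the data cannot support that reading, and Section 8.8 would not warn the reader.

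**Working it through.** The plan states no sample size, effect size or power, so there is no figure of its own to reproduce. The check asks what each contrast would show if timing had no effect at all.

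**Inputs from the documents:** split at the sample mean of disease duration; last-visit score as outcome; baseline scores as candidate covariates; change from baseline as a further analysis; at least one year of treatment; significance at 0.05.

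**Assumptions, none of them in the documents:** mean disease duration 8 years, right-skewed; score rises b = 0.05 or 0.10 points per disease year whenever treatment starts; same 2-point benefit for everyone; score SD 2 around the disease-age trend; follow-up uniform over 1 to 7 years and unrelated to group; baseline reliability 0.5 to 0.8; two-sided test.

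**Step 1. Gap in disease age created by the split.** Gap = mean duration above the mean minus mean duration below it.

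| Assumed distribution (mean 8 years) | Below | Above | Gap (years) |
|---|---|---|---|
| Log-normal, sigma 0.4 | 5.8 | 11.0 | 5.2 |
| Gamma, shape 4 | 5.2 | 11.6 | 6.4 |
| Gamma, shape 2 | 4.4 | 13.3 | 9.0 |
| Log-normal, sigma 0.7 | 4.6 | 14.0 | 9.5 |
| Exponential | 3.3 | 16.0 | 12.7 |

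**Step 2. Unadjusted last-visit gap with no timing effect** = b × gap.
- b = 0.05: 0.05 × 5.2 = 0.26 up to 0.05 × 12.7 = 0.63 points.
- b = 0.10: 0.10 × 5.2 = 0.52 up to 0.10 × 12.7 = 1.27 points.

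**Step 3. After adjustment for one baseline score.** Baseline carries the same disease-age trend but is measured with error, so the residual is approximately b × gap × (1 − reliability). For gamma shape 2:
- b = 0.05: 0.45 × 0.2 = 0.09 to 0.45 × 0.5 = 0.23 points.
- b = 0.10: 0.90 × 0.2 = 0.18 to 0.90 × 0.5 = 0.45 points.

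**Step 4. Change from baseline.** Under this null each patient's change is b × follow-up − 2 plus noise. Disease duration cancels, so the expected group difference is 0.

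**Step 5. Simulation of the same null** (gamma shape 2, 500 runs per scenario, N = 100 and 300):

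| Contrast | b = 0.05: difference; rejection | b = 0.10: difference; rejection |
|---|---|---|
| Last visit, unadjusted | about 0.45; 18–19% (N = 100), 47–52% (N = 300) | about 0.9; 56–60% (N = 100), 96–97% (N = 300) |
| Last visit, baseline-adjusted | 0.08–0.24; 6–17% | 0.17–0.45; 10–56% |
| Change from baseline | about 0; 4–6% | about 0; 4–5% |

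With b = 0 no contrast was biased (rejection 4–7%).

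**Step 6. What each contrast answers.** Baseline at etanercept start can itself be a consequence of delay. Holding it fixed, or subtracting it, removes whatever harm delay has already done by that point. Those contrasts therefore estimate how response to etanercept varies with disease duration. The last-visit level keeps that harm but mixes it with disease age. No planned analysis isolates the effect of referral.

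**The case against.** The plan does not simply compare raw last-visit scores. In Section 8.6 the split at the mean is attached to unadjusted comparisons of the covariates. The effect of early referral is assigned to a regression with both baseline scores among the candidates, and a change-from-baseline comparison is planned as well. In the null above these cut the bias or remove it. Stepwise loss of baseline is also unlikely in a simple setting: in a model with group and one baseline score, baseline was significant in at least 96% of runs at N = 50 and in practically all at N = 100 and 300. Finally, Section 7, the Section 8.1 secondary objective and the word response in the hypothesis already point to the narrower question.

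Much of this stands. A reader might infer that following the plan would report the raw last-visit gap as the effect of early referral. The documents do not support that, because adjusted and change analyses are specified. Nor do they support a claim that the groups lie any particular number of years apart, since no mean, spread or progression rate is given.

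Three things remain. The declared primary outcome is still the last-visit level. Baseline is a candidate and not a fixed term, and even when kept it leaves residual bias because it is measured with error. Most important, the safeguards work by answering a different question from the one in the primary objective.

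**Conclusion.** The point holds as a mismatch between the stated question and what the data can answer, together with an unstated limitation. A worse last-visit score in the delayed group could arise with no timing effect; it does not follow that the plan as written would misreport it.

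The size cannot be derived from the documents. With an assumed mean duration of 8 years and slopes of 0.05 to 0.10 points per disease year, the spurious gap is roughly 0.3 to 1.3 points unadjusted, depending on the duration distribution. It is about 0.1 to 0.45 points after baseline adjustment (gamma shape 2, reliability 0.8 to 0.5) and about 0 for change scores. The zero for change needs the same slope in all patients and follow-up unrelated to group; the plan does not fix the time of the last visit. If scores do not rise with disease age, there is no bias of this kind.

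The data remain useful for the Section 7 question. The correction is inexpensive and should be made.

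**What to change.** 1. Restate the Section 8.1 primary objective and the Section 8.2 hypothesis, in line with Section 7, as the association between disease duration at first etanercept dose and response to etanercept among patients treated for at least 1 year.
2. State in Section 8.3 that disease duration is measured at first dose.
3. In Section 8.6, force baseline BASFI and BASDAI into the regression instead of leaving them to stepwise selection. Disease duration, as the exposure, must stay in for the same reason.
4. Base the conclusion on the baseline-adjusted contrast together with the planned change from baseline, and show baseline means beside last-visit means for each group.
5. State in Section 8.8 that differences in last-visit level are not evidence on early referral.

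The cost is protocol and analysis wording plus one modelling rule. No new kind of variable is required, provided the registry lets duration be dated to first dose, which the documents do not confirm. The downside is a narrower claim than a clinical impact of early referral.

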### 8.2. Setting

#### Patients and Methods

Data will be collected from the Baghdad Teaching Hospital registry. The rheumatology patient registry is a prospective longitudinal multicenter cohort initiated in 2012. It captures all patients treated with biologic therapies managed in the rheumatology department. The decision to initiate and maintain the treatment is guided by the American College of Rheumatology (ACR) recommendations.

#### Study population

Patients will be included in the study if they met the American College of Rheumatology/The European League Against Rheumatism (EULAR) 2019 criteria for AS, with at least 1 year of follow up after starting their first biologic therapy.

Exclusion criteria: patients previously or currently treated with other biological therapies.

#### Hypothesis

There is no difference in response between early and delayed referral to biological treatment.

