### **8.4. Study Size**

There is no pre-identified study size. All patients that meet the inclusion/exclusion criteria will be entered into the study.

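### With 'no difference' as the only hypothesis, p<0.05 as the only criterion and no confidence interval, the plan does not prevent a non-significant result from being read as 'delay does not matter'

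*Combined protocol and SAP*

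**What the plan says.** Under the heading Hypothesis, section 8.2 has one sentence: "There is no difference in response between early and delayed referral to biological treatment". No alternative follows, and no difference is named that would matter clinically.

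Section 8.6 gives one criterion: "P-value <0.05 will be considered statistically significant". For the comparison of patients below and above the mean disease duration it says that "p-values will be generated". Its other planned summaries are descriptive: "Means, medians, standard deviations, or interquartile range as appropriate will be provided for continuous variables". These show the spread of scores among patients, not the uncertainty of a difference between groups. Section 8.6 also plans a stepwise linear regression on last-visit BASFI and BASDAI, and a comparison based on the "difference in change between the baseline of BASDAI and BASFI and last follow-up". No interval is specified for either.

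On size, section 8.4 says "There is no pre-identified study size" and "All patients that meet the inclusion/exclusion criteria will be entered into the study". No expected count, power or precision is given. Section 8.8 lists missing data as the only limitation and does not mention imprecision. No section says how p>=0.05 is to be interpreted.

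**The concern.** A significance test can count against a hypothesis of no difference, but failing to reach significance does not support it. The same p-value can come from a precise estimate near zero or from a wide one that is compatible with a large benefit of early treatment. An interval tells these two cases apart, and the plan has none. Because the only stated hypothesis is 'no difference', a reader following the plan literally could take p>=0.05 as leaving that hypothesis standing, whatever the precision.

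The weakness also runs the other way. If the registry extract is large, p<0.05 alone would not show whether the difference is big enough to matter.

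At stake is the study's main conclusion. Sections 7 and 8.1 ask whether early treatment or referral changes outcome, and the answer could be misread in either direction.

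**Working it through.** The plan states no sample size, SD, target difference or power, so it has no figure to reproduce. The calculation below only illustrates how much a non-significant result could mean at different sizes.

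**From the documents**
- Threshold p<0.05 (section 8.6). Sidedness is not stated; two-sided is assumed.
- Groups cut at the mean disease duration (section 8.6). The resulting split is not given.
- All eligible patients enter (section 8.4). The number is not given.

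**Assumed**
- Total n of 50, 100, 200 or 300.
- A 60:40 split.
- Score SD of 2.0, with 2.5 as a less favourable case.
- A true difference of 1 point.
- An unadjusted comparison of two means, normal approximation.

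**Formulas**
- SE = SD × sqrt(1/(0.6n) + 1/(0.4n))
- 95% CI half-width = 1.96 × SE
- Chance of p>=0.05 = 1 − Φ(1/SE − 1.96)

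**Worked case, n=100, SD 2.0**
- SE = 2.0 × sqrt(1/60 + 1/40) = 0.408
- Half-width = 1.96 × 0.408 = 0.80
- 1/0.408 − 1.96 = 0.489, and Φ(0.489) = 0.69, so the chance of p>=0.05 is 31%

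**Results**

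| n | SE (SD 2.0) | Half-width (SD 2.0) | Chance of p>=0.05 (SD 2.0) | Half-width (SD 2.5) | Chance of p>=0.05 (SD 2.5) |
|---|---|---|---|---|---|
| 50 | 0.577 | 1.13 | 59% | 1.41 | 72% |
| 100 | 0.408 | 0.80 | 31% | 1.00 | 50% |
| 200 | 0.289 | 0.57 | 7% | 0.71 | 21% |
| 300 | 0.236 | 0.46 | 1% | 0.58 | 8% |

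**Cross-check in SD units**, with splits from 50:50 to 65:35. One point at SD 2.0 is 0.5 SD. Power for 0.5 SD is 39–42% at n=50, 67–71% at n=100 and 92–94% at n=200, which agrees with the SD 2.0 column. For a smaller true difference of 0.3 SD, power is 17–18% at n=50, 30–32% at n=100, 53–56% at n=200 and 82–85% at n=400.

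Under these assumptions, p>=0.05 says little about a 1-point difference at n of about 100 or fewer. At SD 2.0 it is fairly informative by n=200 to 300. The documents do not show which case applies, and a p-value alone would not tell the reader.

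**The case against.** The strongest reply is that the sentence in section 8.2 is an ordinary null hypothesis with its label left off. Set beside a p<0.05 threshold, that is the natural reading. Section 7 sets out to evaluate the impact of early initiation, and section 6 expects earlier treatment to help. Nothing suggests a study designed to show equivalence. This stands. A reader might infer that the sponsor intends to report a non-significant result as proof of no effect, but no section says so.

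A reader might also infer that the cohort is small and from one hospital. 'Small' has no support, because no count is given. 'Single hospital' is arguable: section 8.1 names one hospital, while section 8.2 calls its registry multicentre. If the extract holds several hundred patients, a non-significant result could be quite informative.

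Taking every eligible record without a preset size is normal for a retrospective registry study, and recruitment cannot change it. That also stands, and the absence of a target size is not itself the defect. An unknown, fixed n is, however, a reason to report an interval.

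It is also true that group summaries and a regression yield effect estimates, and that adjusting for baseline score would usually narrow the interval relative to the table. But the plan asks for no interval around those estimates. Its regression lists disease duration in years rather than the early/delayed groups, and stepwise selection could drop the term of interest.

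Finally, a formal margin for 'no important difference' would need clinical justification. It could probably no longer be prespecified: data collection was planned to end on 01 October 2020 and this version is dated 29 July 2021. That is a good reason not to require one. It does not weaken the case for an interval.

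**Conclusion.** The point holds as a gap in the plan, not as a prediction of how the results will be reported. The only hypothesis is an unlabelled 'no difference', the only criterion is p<0.05, no interval is planned and no size or precision is stated. The plan therefore does not guard against reading an imprecise non-significant result as absence of effect.

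How much this matters depends on an n that the documents do not give. For a true 1-point difference with a 60:40 split, the chance of a non-significant result falls from 59% at n=50 to 1% at n=300 if the SD is 2.0, and from 72% to 8% if it is 2.5. The n, SD, split and difference are all assumptions, and the comparison is unadjusted. The need for an interval does not depend on them, because the interval is what would show which situation the study is in.

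**What to change.** **Section 8.2.** Label the sentence as the null hypothesis and state the alternative, namely that response differs between early and delayed patients.

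**Section 8.6.** For BASDAI and for BASFI, report the early-minus-delayed difference with its 95% CI from one fixed linear model per outcome. Force in the early/delayed term and the baseline score, so that neither is subject to stepwise selection. Name any further covariates in the text rather than selecting them from the data. Add that p>=0.05 alone is not evidence of no difference, and that the conclusion rests on the range of differences the CI excludes.

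Do not require an equivalence margin.

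**Cost.** A few sentences, one additional model per outcome and no new data. The downside is that some results that would have been called 'no difference' will have to be called inconclusive.
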